### Power analysis

Relevant data (means  $\pm$  standard deviations) demonstrating the effects of moderate-to-severe energy deficit on lean body mass were used to determine statistical power and sample size. The percentage total body mass loss (2.7 kg) attributed to lean body mass during a 21-d, higher-protein (1.6 g·kg $^{-1}$ ·d $^{-1}$ ), moderate energy deficit was approximately 30% (0.8 kg). However, the proportion of total body mass loss (5.8 kg) attributed to lean body mass in response to a short-term (~7-d), military training-induced, severe energy deficit was approximately 55% (3.1 kg) (unpublished data). Based on these results, and given the proposed study will induce a 55% energy deficit for 28 days in men consuming a higher-protein diet (1.6 g·kg $^{-1}$ ·d $^{-1}$ ), lean body mass will likely account for 40% of the total body mass loss. Maintaining testosterone within normal physiological ranges is expected to attenuate the loss of lean body mass by 25%, such that those assigned to the testosterone group will lose proportionally 30%, the same percentage of lean body mass as demonstrated in our previous study. Based on these estimates, the sample size necessary to determine the estimated differences between treatments is 22 per group. However, based on previous variability in lean body mass loss in response to moderate-to-severe energy deficit, 25 participants per group is a more conservative estimate to allow for detection of treatment effects in the current study. To account for possible attrition (20%), 30 participants will be assigned to each group (60 total participants). To successfully enroll 60 participants, we request the ability to consent up to 240 participants, given only a third of those briefed and consented in past projects, with more lenient study-specific eligibility criteria, were enrolled. **At least 50 participants will complete the intervention and enrollment will stop once 50 participants have completed the study.**

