## IRB Review History

### Executive Summary

Energy deficit during military operations is often ~50% of total daily energy requirements and can reach near complete starvation. The physiological consequences of severe energy deficit include physical performance decrements, particularly energy deficit-induced hypogonadism and the loss of lean body mass, which cannot be overcome with macronutrient modification alone. Prolonged energy deficit also impacts mood, attentiveness, and decision-making capabilities. The extent to which energy deficit-induced hypogonadism contributes to physiological and psychological declines during sustained energy deficit remains poorly understood. Therefore, the objective of this study is to determine whether maintaining a eugonadal state during severe, sustained energy deficit attenuates physiological decrements, particularly the loss of lean body mass, and maintains mental performance. To address these objectives and more (e.g., gut health, appetite regulation, physiological and psychological recovery), we will enroll up to 60 physically active men in a 3-phase, randomized, placebo-controlled study.

After completing a 14-day (**free-living, phase 1**), energy-adequate, diet acclimation phase (protein,  $1.6 \text{ g} \cdot \text{kg}^{-1} \cdot \text{d}^{-1}$ ; fat, 30% total energy intake; with remaining energy derived from carbohydrate), participants will be randomized to one of two experimental groups and undergo a 28-day (**live-in, phase 2**), 55% energy deficit phase: energy deficit alone (DEF) or energy deficit + exogenous testosterone (DEF+TEST). Recovery (**free-living, phase 3**) will be assessed after completing phase 2 to determine when body mass has been recovered within  $\pm 2.5\%$  of initial body mass (duration will vary, 42-day maximum for phase 3). Body composition, state-of-the-art stable isotope methodologies, proteomics, metabolomics, muscle biopsies, whole-room calorimetry, molecular biology, activity/sleep monitoring, personality and cognitive function

assessments, functional MRI (fMRI), biochemistries, and rigorously controlled diet and physical activity will be used to assess physiological and psychological responses to energy restriction and recovery feeding while in a hypogonadal versus eugonadal state. Results of the proposed experiments will provide a basis for future studies aimed at improving Warfighter resiliency to and recovery from negative energy balance.

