**Table 2. Power Analysis and Sample Size Justification**

**Hypothesized Effect (mean  $\pm$  SD)**

$\Delta$ Lean body mass following the 28-d intervention, kg	
DEF	$3.0 \pm 0.75$
DEF+TEST	$2.25 \pm 0.75$
Effect Size	1.0
Alpha	0.05
Power	0.90
Sample Size	22 per group
Expected variability	25 per group
20% study attrition	60 participants total
75% eligibility screen failure	240 total consented individuals

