**Enrollment will stop once 50 participants (25 per group) complete the intervention**

## Study Timeline

Individuals who respond to recruitment materials and indicate interest in study participation will be provided with study-specific information. If still interested, potential participants will be asked a series of demographic and health-related questions to assess eligibility via phone/web-based methods (approximately 15 min). Individuals who meet the initial inclusion/exclusion criteria via **self-reported** responses will be invited to attend two screening visits at Pennington Biomedical Research Center (PBRC). Details of each study visit are described below. See Train Schedule in **Appendix A**.

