## Randomization

Immediately following phase 1 testing on day 14, participants will be randomized to one of two experimental groups, either a 28-d (live-in), 55% energy deficit phase (DEF) or a 28-d (live-in), 55% energy deficit phase with exogenous testosterone administration (DEF+TEST). A randomization scheme will be determined using a block design (n=60) and age stratification (< 29 years or ≥ 29 years). Randomization will be done by a biostatistician with no direct study affiliation. Prior to the start of the study, the randomization schedule will be given to the pharmacist. The PBRC clinical research pharmacist will have no direct contact with participants. Treatment administration will be performed by a physician assistant, nurse practitioner, or nurse who will not be aware of treatment assignments. Participants and all study personnel will be blinded to treatment group. The code will be kept as a locked electronic file on a secure server by the pharmacist until study completion or there is a need to break the code for safety of the participant.

## Phase 2: 55% Energy Deficit (live-in diet & activity control). Day 15–Day 42

- During the energy deficit phase, participants will live on Pennington Biomedical's inpatient unit in a 24-hour-a-day controlled setting. Once a day, participants will have their vitals (BP, pulse) measured. All meals will be eaten on the unit and monitored. Daily, participants will be weighed. Additionally, a wrist-worn accelerometer will be used throughout phase 2.
- Throughout phase 2, participants will complete supervised exercise sessions 1-4 times per day. Every 2 weeks, participants will undergo submax met carts for each mode of exercise utilized.
- Participants will consume 100 mL/d  $^2\text{H}_2\text{O}$  (i.e., heavy water) from day 15 to 42.
- Participants will be asked to provide a saliva sample on days 15, 19, 23, 27, 31, 35, and 39 to assess body water enrichment.
- Blood draws will occur on days 28 and 42.
- Cognitive testing will be performed on days 15, 20, 22, 27, 29, 34, 36, 40 and 41 over a 1.5-2 hour period each day.
- A DXA scan will be done on days 28 and 39.
- A 1 hour fMRI will be done on days 36, 37, and 38.
- An injection (placebo or testosterone) will be administered on days 15, 21, 28, and 35.
- Eating Inventories (TFEQ, FCI, FCI trait) will be completed on day 42.

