### **Stopping Rules**

There is more than minimal risk for participating in this trial. Nevertheless, in addition to monitoring recruitment and compliance to the intervention, we also will monitor the rates of injury in our participants. The safety officers, in conjunction with the study investigators, will alert the IRB and DSMB if a larger than reasonably expected injury rate occurs in the treatment groups. Other issues that are related to the stopping rules include:

- New information – It is unlikely that new information will become available during this study that would result in discontinuing the trial.
- Limits of assumption – It is possible that the value of data analysis will be limited by differences between the intervention groups at baseline or because of study dropouts or missing data. Baseline differences will be analyzed annually and effects on the power to detect differences in the outcome measures will be evaluated and discussed with the PI, safety officer, and the USARIEM Project Officer. Although an excessive number

of dropouts could occur, this has not been our past experience. In similar studies completed by USARIEM, the dropout rate was approximately 10%. If the dropout rate for the proposed study exceeds 20%, the safety officer will initiate a meeting with the PI to discuss strategies to increase retention. If the dropout rate exceeds 50%, the safety officer will meet with the study investigators to determine whether or not the study should continue.

- Limit of rules – We acknowledge that circumstances, other than what are listed, may justify stopping the study.

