### **Withdrawal of Subjects**

We will attempt to retain program participants once randomized at a retention rate of 80% for study completion through Day 42 and close-out visit. It is our desire to analyze results on all participants who were included into the program (e.g. completed SV1 visit). In accordance with the declaration of Helsinki/Tokyo/Venice/Hong Kong, participants have the right to withdraw from the program at any time for any reason. The investigator also has the right to withdraw participants from the program treatments in the event of inter-current illness, adverse experience, treatment failure, protocol violation, or other reasons. Should a participant decide to withdraw from treatment, all efforts will be made to complete and report follow-up observations as thoroughly as possible.

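### Sixty randomised at the stated 20% attrition gives 48 expected completers (24 per group), not the 50 (25 per group) the plan states; power at the Table 2 effect and SD stays above 90%

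*Combined protocol and SAP*

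**What the plan says.** The Power analysis section and Table 2 build the sample size in steps. A difference of 0.75 kg in lean-mass loss with an SD of 0.75 kg (effect size 1.0), alpha 0.05 and power 0.90 gives 22 per group. This is raised to 25 per group because of variability seen in earlier work. Then comes the attrition step: "To account for possible attrition (20%), 30 participants will be assigned to each group (60 total participants"). Table 2 repeats it in a row labelled "20% study attrition", with 60 participants in total.

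The section closes with a firm count and a stopping rule for enrolment: "At least 50 participants will complete the intervention and enrollment will stop once 50 participants have completed the study". The line directly below Table 2 gives the split: "Enrollment will stop once 50 participants (25 per group) complete the intervention".

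Two other places fix the number available. The Executive Summary says "we will enroll up to 60 physically active men", and the Randomization section says "A randomization scheme will be determined using a block design (n=60) and age stratification". The Stopping Rules section reports past experience: "In similar studies completed by USARIEM, the dropout rate was approximately 10" percent.

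**The concern.** The attrition percentage, the number assigned and the number of completers are three linked figures, and any two determine the third. Here they do not agree. If 20% of 60 are lost, fewer than 50 remain, and nothing in the plan provides for a 61st participant to make up the difference.

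At stake is whether the completer count can be relied on. The sample size justification states that count as an outcome, and the enrolment stop is tied to it. Both stand beside an attrition allowance that does not deliver it. The 25 per group also has a purpose, since it is the plan's cushion against a larger SD than assumed. A shortfall in completers comes out of that cushion.

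**Working it through.** **Inputs.** Difference 0.75 kg (3.0 minus 2.25), SD 0.75 kg, alpha 0.05, power 0.90, 22 then 25 per group, 20% attrition, 60 total (Power analysis, Table 2). Two-sided testing (Objective I: Statistics). Limit of 60 (Executive Summary, Randomization). Past dropout about 10% (Stopping Rules).

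**Step 1: reproduce the base figure.** Effect size d = 0.75 / 0.75 = 1.0. For a two-sided two-sample t-test with n per group, power comes from the noncentral t distribution with 2n − 2 degrees of freedom and noncentrality d × √(n/2). Solving for 90% power gives n = 22.02, and power at n = 22 is 0.8997. The plan's 22 per group at 90% therefore reproduces.

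**Step 2: reproduce the attrition figure.**

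| Calculation | Per group | Total |
|---|---|---|
| Plan | 30 | 60 |
| n × (1 + 0.20) | 25 × 1.2 = 30 | 50 × 1.2 = 60 |
| n / (1 − 0.20) | 25 / 0.8 = 31.25 | 50 / 0.8 = 62.5 |

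The plan's 60 matches only the multiplication. In whole participants, the division gives 63, or 64 for equal groups.

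**Step 3: compare with the next row of Table 2.** That row takes 60 to 240 for a 75% screen-failure rate. Since 60 / (1 − 0.75) = 240, the loss is handled there by division. Multiplication would have given 60 × 1.75 = 105. Two adjacent rows therefore treat a loss percentage differently.

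**Step 4: work forward from 60.**

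- At 20% attrition: 60 × 0.80 = 48, or 24 per group.
- Largest attrition that leaves 50: 1 − 50/60 = 16.7%.
- At 10% dropout: 60 × 0.90 = 54.

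**Step 5: power, by the Step 1 method.** At d = 1.0:

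| Completers per group | Power |
|---|---|
| 22 | 90.0% |
| 24 | 92.4% |
| 25 | 93.4% |

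**Step 6: the variability margin.** The documents give no SD other than 0.75 kg for this comparison, so the larger values below are assumptions, with the difference held at 0.75 kg.

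| Assumed SD (kg) | Power at 24 per group | Power at 25 per group |
|---|---|---|
| 0.75 | 92.4% | 93.4% |
| 0.80 | 88.9% | 90.1% |
| 0.85 | 84.9% | 86.4% |
| 0.90 | 80.7% | 82.3% |

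Power stays at 90% up to an SD of about 0.80 kg with 25 per group, and up to about 0.785 kg with 24.

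**The case against.** The strongest reply is that this hardly matters. The gap is two completers, one per group. The 20% is described as possible attrition, so it is an allowance and not a forecast. Past dropout of about 10% would leave 54. Power at the planned effect exceeds 90% either way. All of this stands, and it is why the point is minor. It does not make the three figures agree.

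A second reply is that enrolment simply continues until 50 have completed. The plan does not provide for that, because enrolment goes up to 60 and the randomisation scheme is drawn up for 60. The Stopping Rules section calls for a retention meeting only when dropout exceeds 20%, so attrition between 16.7% and 20% would miss 50 without triggering it.

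A third reply is that 20% was meant as over-recruitment relative to 25. The label in Table 2 is attrition, and the next row divides, so that reading is weak.

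A reader might also infer more than the figures support:

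- **That the trial is underpowered.** At Table 2's difference and SD, 24 per group gives 92.4%. A fall below 90% needs an SD above about 0.785 kg, which the documents do not assume.
- **That the stop should come down to 48.** A stopping count is a ceiling and need not equal an expected value. Lowering it would give up the 25 per group chosen for variability even when 50 can be reached.

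**Conclusion.** Wrong as written, and minor. The plan allows for 20% attrition by multiplying by 1.2 where it should divide by 0.8. Sixty randomised at 20% attrition gives 48 expected completers (24 per group), against a stated minimum of 50 (25 per group). The number randomised covers attrition of up to 16.7%.

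The planned 90% power is kept, but only on Table 2's own assumptions of a 0.75 kg difference and an SD of 0.75 kg, and for the simple two-group comparison that reproduces the 22. The cost is one of the three participants per group added for variability. If dropout is near the 10% seen before, the shortfall does not arise in expectation. The attrition arithmetic itself needs no assumption beyond the plan's stated 20%.

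**What to change.** Keep 60 randomised and keep the enrolment stop at 50 completers (25 per group). In the Power analysis section and Table 2, replace the 20% attrition line with text to this effect: 60 randomised yields 50 completers if attrition is at most 16.7%; at 20% attrition, 48 (24 per group) are expected, with power about 92% at the Table 2 effect and SD. Reword the sentence that at least 50 will complete so that 50 is a target.

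This is a wording change in two places. It leaves the number randomised, the randomisation scheme, the visit schedule and the stopping count as they are. Raising the total to 63 or 64 would also reconcile the figures, but it would mean changing the enrolment limit and the randomisation scheme, and the power at the planned effect does not call for it.

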**Table 2. Power Analysis and Sample Size Justification**

**Hypothesized Effect (mean  $\pm$  SD)**

$\Delta$ Lean body mass following the 28-d intervention, kg	
DEF	$3.0 \pm 0.75$
DEF+TEST	$2.25 \pm 0.75$
Effect Size	1.0
Alpha	0.05
Power	0.90
Sample Size	22 per group
Expected variability	25 per group
20% study attrition	60 participants total
75% eligibility screen failure	240 total consented individuals

**Enrollment will stop once 50 participants (25 per group) complete the intervention**

## Study Timeline

Individuals who respond to recruitment materials and indicate interest in study participation will be provided with study-specific information. If still interested, potential participants will be asked a series of demographic and health-related questions to assess eligibility via phone/web-based methods (approximately 15 min). Individuals who meet the initial inclusion/exclusion criteria via **self-reported** responses will be invited to attend two screening visits at Pennington Biomedical Research Center (PBRC). Details of each study visit are described below. See Train Schedule in **Appendix A**.

### Screening Visit 1. SV1

- The study consent form will be reviewed with the participant to ensure all questions and concerns are clarified before the participant signs the consent form and before any procedures are conducted. Those who are still interested in participating will be asked to sign the consent form.
- Height, weight, blood pressure, and pulse will be measured. Participants who do not meet the height/weight criteria will have eligibility assessed by neck and waist circumference measurements to estimate percent body fat according to Army Regulation 600-9 (**Appendix B**). Circumference measurements will not be repeated during the study.
- A Physical Activity Readiness Questionnaire (PAR-Q) will be administered and CVD risk stratification assessed.
- Information regarding the participant's current medications and medical history will be recorded.
- A study dietitian will meet with the participant to discuss current eating habits and dietary requirements for each phase of the study.
- Eligibility criteria will be reviewed. All participants who maintain eligibility criteria will be scheduled for an appointment approximately 1 week later for Screening Visit 2.

### Screening Visit 2. SV2

- The participant will have an EKG and a complete physical exam.
- Weight, blood pressure, pulse, and head size will be measured.
- Fasting blood will be drawn for CBC, Chem 26, PSA, testosterone, and study archives.
- Urine will be collected for a urinalysis and urine drug screening.
- A barriers interview will be conducted (**Appendix C**).
- A Three Factor Eating Questionnaire (TFEQ), or equivalent measure, will be administered to exclude restrained eaters.
- Information regarding any changes in medications or any adverse events will be recorded.
- Eligibility criteria will be reviewed. All participants who maintain eligibility criteria will be provided an accelerometer to wear, will complete a 3 day physical activity log, and will complete a 3-day food record (2 weekdays, 1 weekend day) one week prior to the start of phase 1. An appointment will be scheduled for Day 0 within 45 days of SV2.

- If more than 45 days lapse between screening measures and D0 scheduled date, participants may be asked to repeat measures to re-assess eligibility.

**Phase 1: Diet Acclimation (free-living). Day 0–Day 14**

- During the diet acclimation phase, participants will return to Pennington Biomedical once a day to eat and receive additional meals for the day. Participants will be weighed daily and caloric adjustments made if needed. Participants will be asked to record their activity daily throughout the phase. Additionally, 2 accelerometers (wrist- and waist-worn) will be applied at Day 0 and worn through day 14.
- Blood draws will occur on days 0, 7, and 14.
- Cognitive training will be performed on days 0, 2, 4, 6, 8, and 10 for approximately 1.5-2 hours each day. Cognitive testing will be performed on days 5 and 13 over a 2-hour period each day. The timing of training sessions is not critical.
- A DXA will be done on days 0 and 11.
- A 1-hour fMRI will be done approximately on days 5, 9, and 12.
- A food intake test with VAS and gut hormone assessments will be done on day 7.
- Participants will consume 150 mL/d  $^2\text{H}_2\text{O}$  (i.e., heavy water) from day 0 to 7 and 100 mL/d  $^2\text{H}_2\text{O}$  from day 8 to 14.
- Participants will be asked to provide a saliva sample on days 3, 7, and 11 to assess body water enrichment.
- Participants will ingest D3-creatine (D3Cr) (60 mg capsule) on day 11 for estimates of muscle mass at the end of phase 1 (urine collections on days 11, 13, 14).
- On day 11, participants will stay in the metabolic chamber and have urine nitrogen and urine creatinine collected for 24 hours.
- Participants will consume 2 g sucralose dissolved in 180 mL water on the morning of study day 11. A 24-hour urine sample collected with the nitrogen and creatinine testing will be used to analyze the sugar substitute ingestion.
- Participants will be asked to provide a stool sample on day 11 (+72 hours) for gut microbiome analysis.
- Information regarding adverse events will be collected on days 0, 7, and 14.
- A biodex familiarization test will be performed on day 0 and the actual biodex test will be performed on day 13.
- A VO2max treadmill test will be performed on day 0. The test will be used to prescribe exercise intensities.
- Eating Inventories (TFEQ, FCI, FCI trait) will be completed on day 14.
- A bike familiarization ride will be performed within the first week of Phase I. The familiarization ride will be used to establish appropriate settings and exercise workloads for the experimental testing procedures.
- Muscle biopsies will be collected pre, 60 min and 360 min post a 60 min cycle ergometry exercise session on day 14.
- Time commitment during phase 1 will be about 34 hours per day on days 0-6, 8-10 and 12-13. On day 7, the time commitment will be about 4 hours. On days 11 (whole-room calorimetry day) and 14 (end of phase 1, check into PBRC metabolic ward after testing), participants will be at the facility for 24 hours.

- Participants will be randomly assigned to 1 of 2 experimental groups on day 14.

